7.9. Sample size

A meta-analysis of six studies investigating the impact of kcal labelling on energy consumed from a single food did not demonstrate a statistically significant effect [11]. However the designs of these studies were different from the present study: the food options were mainly snacks (only one study offered to consume main meals [38]) and participants were not aware of the amount of kcal they actually consumed (the label was placed on the container or packaging, adjacent to the food, or presented on a display board). In our design, we expect a significant effect of kcal labelling with a reduction of 8.4% of self-served energy per meal may occur, which is the effect size found in a meta-analysis investigating the impact of kcal labelling on energy consumed during a meal with a range of available food options – i.e., the most similar design to the present study. The most up to date evidence of an effect of PACE labelling on energy consumed from foods/drinks is a meta-analysis of two studies and showed a significant reduction of 14.4%. Due to the small number of participants included in this meta-analysis, we conservatively powered our study to be able to detect an 8% reduction for both type of labels (kcal, PACE or kcal and PACE).

We will run a two-level mixed model including 18 trials (level 1) per participant (level 2) and compare self-served energy in each of the four trial arms (control, kcal labelling, PACE labelling, kcal and PACE labelling). We estimate SD of 300 kcal for self-served energy at level 1 and level 2 based on average SD of energy consumed during experimental meals [11]. A sample size of 1,600 participants with $\alpha = 0.05$ will allow to detect a 8% energy reduction between any of the four groups at power = 0.80. It will also allow to detect a small effect ($f=0.07$) of the interaction between the interventions and higher educational qualification education at power = 0.80 (MLPowSim) [39].

In a previous study we conducted at virtual fast food restaurants [40], we found small-to-medium correlation between level of education and healthiness motivation ($r=0.17$) and small-to-medium correlation between healthiness motivation and kcal ordered ($r=-0.25$). Because evidence of a relationship between SEP and physical activity is mixed [41], we hypothesize small-to-medium correlation. Empirical estimates of sample sizes needed for 0.8 power in mediation analyses indicate that samples of ≈ 380 are sufficient to detect mediation through pathways that are small and small-to-medium in statistical size using bias-corrected bootstrap tests [42]. Thus, a sample of 1,600 participants (i.e., 400 per experimental condition) would allow for adequate power in our planned moderated mediation analysis.

We will recruit a sample of 1,800 participants (who consent to take part in the study) to account for potential data loss due to dropouts and failed quality controls (approx. 10%) resulting in a minimum sample of 1,600 participants for analyses. However, if we experience a greater loss of data than

expected, we will continue to recruit participants until we achieve the required sample size of 1,600 participants.

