2. OBJECTIVES, OUTCOMES MEASURES AND HYPOTHESES

OBJECTIVES	OUTCOME MEASURES	HYPOTHESES

Primary objective
 
To investigate the effect of labelling (kcal or PACE) on the total self-served energy among participants of lower and higher SEP.
	
Total self-served energy in kcal from hypothetical meals
	
Labelling (kcal or PACE) will influence the size of self-served portion and result in reduced total self-served energy among both participants of lower and higher SEP.
 
Kcal and PACE labelling will exert a stronger effect on self-served energy among participants of higher compared to lower SEP.

		PACE labelling will exert a stronger effect on self-served energy than kcal labelling.
Secondary objectives To investigate the psychological processes that may explain the different effect of the intervention and whether health motivation and physical activity level mediate the differential effect of labelling (kcal or PACE) on total self-served energy among participants of lower and higher SEP.	Executive function (tasks) Health motivation in food choices (questionnaire)	Participants of higher SEP will have better executive function than participants of lower SEP, which will moderate the relationship between SEP and the effect of energy/PACE labelling on the total energy of the selected meal. Kcal/PACE labelling will exert a stronger effect on self-served energy among participants of higher SEP because they will be more motivated by health in their food choices than participants of lower SEP.

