7.5. Main analyses

The primary aim of the statistical analyses will be to test the effect the labelling intervention and SEP on self-served energy. Secondary analyses will be run in order to investigate the role of potential mediators to explain the relationship SEP-self-served energy. The measure of SEP used in our main analyses will be the *highest educational qualification* (binary variable: *lower vs. higher*) because previous research showed that people of higher education were more likely to use nutrition labels [35], [36].

² MET-minutes: Metabolic Equivalent of Task of an activity × minutes performed.

Linear mixed effect models will be run in order to test the effect of the labels and of highest educational qualification on the self-served energy, with participants and dishes set as random effects to account for correlation between repeated measures by the same participant and across the different food items. The main model will test the effect of the labelling intervention (four levels: kcal labelling, PACE labelling, kcal and PACE labelling, no labelling), highest educational qualification (two levels: lower, higher) and the interaction between labelling intervention and highest educational qualification. If the interaction is significant, analyses will be stratified by *highest educational qualification (lower and higher)* and two linear mixed models will be fitted to examine the effect of the labelling intervention on self-served energy.

If there is a main effect of the labelling intervention in one of the above linear mixed models we will follow up this main effect by conducting the following pairwise comparisons:

- Self-served energy in each of the three labelling conditions compared to no labelling condition:
 - o No labelling vs. kcal labelling
 - o No labelling vs. PACE labelling
 - o No labelling vs. kcal and PACE labelling combined
- Self-served energy in the combined labelling condition compared to single labelling conditions
 - o Kcal and PACE labelling combined vs. kcal labelling
 - o Kcal and PACE labelling combined vs. PACE labelling
- Self-served energy in one single labelling condition compared to the other single labelling condition:
 - o Kcal labelling vs. PACE labelling

We will apply a Bonferroni correction to the level of significance based on the number of pairwise comparisons made (e.g., 12 comparisons: $0.05/12=0.004$).

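### Section 7.9 gives 80% power at alpha 0.05 for pairwise differences that Section 7.5 tests at 0.05/6, where the same effect has about 57% power

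*Combined protocol and SAP*

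**What the plan says.** Section 7.9 (Sample size) plans on an 8% reduction for each type of label, with 400 participants per arm and 18 dishes each. It says that 1,600 participants, at alpha 0.05, "will allow to detect a 8% energy reduction between any of the four groups at power = 0.80". It mentions no multiplicity adjustment.

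Section 7.5 (Main analyses) first tests labelling as a four-level factor. If that test is significant, "we will follow up this main effect by conducting the following pairwise comparisons". The list has six entries: each of the three label arms against no label, the combined label against each single label, and kcal against PACE. On the significance level it says: "We will apply a Bonferroni correction to the level of significance based on the number of pairwise comparisons made". The only worked example is 12 comparisons at 0.05/12, which fits six contrasts in each of two education strata. The level for the pooled model, 0.05/6, is not printed but follows from the rule.

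Section 2 lists among the primary hypotheses that "PACE labelling will exert a stronger effect on self-served energy than kcal labelling". One of the six corrected contrasts decides it.

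**The concern.** The same contrasts are powered at one significance level and tested at a stricter one. The overall 3-df labelling test does use 0.05, but it is a different test: it cannot say which label works or whether PACE beats kcal, and Section 7.9 does not state its power.

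The risk is in interpretation. A label contrast that misses significance at 0.0083 would be read against a printed 80%, as fairly strong evidence against an 8% effect. The matching figure is much lower, so a null result would carry less weight than the plan suggests.

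A related gap makes the 80% uncheckable: the effect is a percentage and the SDs are in kcal, but no control mean links them.

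**Working it through.** **Inputs.** From Section 7.9: alpha 0.05, power 0.80, 8% reduction, 400 per arm, 18 dishes, and "We estimate SD of 300 kcal for self-served energy at level 1 and level 2". From Section 7.5: six contrasts, Bonferroni. Assumption: two-sided tests, since sidedness is not stated.

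**Can the printed 80% be reproduced?** Only by solving for the missing control mean.
- Variance of a participant's 18-dish mean: 300² + 300²/18 = 95,000, so SD = 308.2 kcal.
- SE of a difference between two arms: 308.2 × √(2/400) = 21.79 kcal.
- Detectable difference at 80% power, two-sided 0.05: (1.960 + 0.842) × 21.79 = 61.1 kcal.
- This is 8% of 61.1/0.08 = about 763 kcal per dish (about 677 kcal if one-sided).

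Neither mean is in the documents. Both are possible on a 20–1000 kcal task.

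**Power at the level that will be used.** This step needs neither SD nor control mean. An effect with 80% power at two-sided 0.05 has a standardised size of 1.960 + 0.842 = 2.802. The critical value at 0.05/6 is 2.638.
- Power per contrast: Φ(2.802 − 2.638) = Φ(0.164) = 0.565.
- Reduction with 80% power: 8% × (2.638 + 0.842)/2.802 = 9.94%.
- Participants needed to keep 80% for 8%: 400 × (3.480/2.802)² = about 617 per arm, or about 2,470 in total.

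In 400,000 simulated trials the power per contrast was 0.565, and 0.563 when the overall test also had to be significant.

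**Could the 0.80 already include the correction?** With the stated SDs, 80% at 0.05/6 needs a control mean of (3.480 × 21.79)/0.08 = about 948 kcal, and at 0.05/12 about 1,010 kcal. The first is close to the 1000 kcal maximum and the second exceeds it. The text also says alpha 0.05.

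**Overall test and combined results, all three labels at 8%.** The noncentrality is 0.75 × 2 × 2.802² = 11.8 on 3 df, giving power 0.83. In the simulation:
- at least one label separates from control (after the overall test): 0.80;
- all three separate: 0.31 with Bonferroni, 0.37 with Holm, 0.61 uncorrected;
- per contrast with Holm: 0.594.

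**Sensitivity to the control mean (assumed values, SDs as stated).**

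| Control mean, kcal | Power at 0.05 | Power at 0.05/6 |
|---|---|---|
| 500 | 0.45 | 0.21 |
| 600 | 0.60 | 0.33 |
| 700 | 0.73 | 0.47 |
| 800 | 0.84 | 0.62 |
| 900 | 0.91 | 0.75 |

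**Sensitivity to the anchor.** If the simulated 0.80 was really 0.79 or 0.81, power at 0.05/6 is 0.55 or 0.58. If everything is one-sided it is 0.54. If the 80% was one-sided but the contrasts are tested two-sided, it is 0.44.

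**Two scenarios.**
- PACE against kcal: the reductions cited in Section 7.9 are 14.4% and 8.4%, a gap of 6 points. The standardised size is 2.802 × 6/8 = 2.101. Power is Φ(2.101 − 1.960) = 0.56 at 0.05 and Φ(2.101 − 2.638) = 0.30 at 0.05/6.
- Stratified by education, about 200 per arm: the standardised size is 2.802/√2 = 1.981. Power is Φ(1.981 − 2.865) = 0.19 at 0.05/12 and Φ(1.981 − 2.638) = 0.26 at 0.05/6. An effect 1.5 times as large has 0.54 or 0.63; twice as large, 0.86 or 0.91.

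**The case against.** The strongest reply is that no printed figure is shown to be miscalculated. Section 7.9 is open about its level: "A sample size of 1,600 participants with $\alpha = 0.05$ will allow to detect a 8% energy reduction". On that view the 57% is conditional on an 80% that nobody can verify. This stands in part. The 57% is what the plan's own claim implies, not an independent estimate of power. The SDs are also open to another reading: if 300 kcal is a total SD, with an assumed within-participant correlation of 0.5, power at 0.05/6 would be 0.68 at a control mean of 600 kcal and 0.84 at 700. But whatever the inputs, power at 0.05 is not power at 0.05/6.

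A second reply is that the impact is moderate: in the planned scenario the overall test has 83% power and at least one label separates from control in 80% of trials. That is true. However, Section 7.9 claims 80% for a difference between any pair of arms, not for at least one success. The 31% for all three labels is a target the plan never set, and even uncorrected it would be only 61%.

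Third, the PACE-against-kcal figures use an effect the authors declined to plan on. They wrote that "we conservatively powered our study to be able to detect an 8% reduction for both type of labels" because the PACE evidence came from few participants. Section 7.9 likewise claims no pairwise power within education groups. Both sets of figures are illustrations, not errors in the plan.

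Finally, Bonferroni is valid and prespecified. Holm is an improvement, not a correction of the misstatement.

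**Conclusion.** The concern holds. The 80% in Section 7.9 does not belong to the pairwise tests in Section 7.5. Taking the printed 80% at two-sided 0.05 as correct, power for one given pooled contrast is about 57%, and 80% power needs a reduction of about 9.9% instead of 8%. These two figures depend on no SD or control mean, but they do depend on that anchor. Actual power depends on a control mean and a choice of sidedness that the documents do not give. The error lies in the stated power; the validity of the tests is not in question. It should be fixed before the results are interpreted.

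**What to change.** Keep 1,600 participants and revise the text as follows.

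1. In Section 7.9, state the control mean that converts 8% into kcal, the detectable difference in kcal, and whether the test is one- or two-sided. Confirm that this mean and the two SDs suit the 20–1000 kcal task.
2. Restate pairwise power at the level Section 7.5 applies, and print 0.05/6 for the pooled model. If the inputs in item 1 confirm the existing 80% at two-sided 0.05, the figures are about 57% for an 8% reduction, or 80% for about 9.9%. If they do not, recompute.
3. Report the power of the 3-df labelling test separately (about 83% on the same anchor if all three labels give 8%).
4. Add the stratified analysis as a labelled scenario, with about 200 per arm.
5. Preferably, replace Bonferroni with Holm in Section 7.5. Holm controls the same familywise error rate and is never less powerful. Per-contrast power rises from 0.565 to 0.594 if all three labels work equally.

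The cost is wording in Section 7.9 and one sentence in Section 7.5. No extra participants are needed, but the stated pairwise power becomes less favourable.

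### The 0.80 power for an 8% difference is stated at alpha 0.05, but the pairwise contrasts, including PACE v kcal, are tested at a Bonferroni level where power for 8% is about 0.56 or lower

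*Combined protocol and SAP*

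**What the plan says.** Section 2 lists three hypotheses under the primary objective. The third is that "PACE labelling will exert a stronger effect on self-served energy than kcal labelling".

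Section 7.5 tests it as one of six pairwise contrasts, "Kcal labelling vs. PACE labelling", run if the labelling main effect is present. All the contrasts share a Bonferroni correction set by how many are made. The only worked example there is twelve comparisons, giving 0.004. If labelling interacts with education, the model is refitted separately in the lower and higher education groups.

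Section 7.9 cites an 8.4% reduction for kcal labels. For PACE it cites "a meta-analysis of two studies and showed a significant reduction of 14.4"%, then sets that figure aside because few participants contributed to it, saying "we conservatively powered our study to be able to detect an 8% reduction for both type of labels". The closing power statement is at alpha 0.05: the sample "will allow to detect a 8% energy reduction between any of the four groups at power = 0.80". Section 7.9 gives no power at a corrected alpha and no planning difference for PACE against kcal.

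**The concern.** Two things do not line up. First, the significance level in the power statement is not the level at which section 7.5 judges the contrasts that the statement describes. A reader will take 0.80 as the chance that a true 8% difference between two groups is declared significant. Under the plan's own rule that chance is lower.

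Second, the 8% was chosen from effects of a label on energy. It is a cautious choice for label v no label, being a little under the 8.4% cited for kcal and well under the 14.4% cited for PACE. The same 8% is not cautious as a difference between two active labels. With kcal at the cited 8.4%, PACE would have to reduce energy by 8.4 + 8 = 16.4 points to be 8 points better. That is more than the 14.4% which the plan already declines to rely on.

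At stake is how a null result on a primary hypothesis is read. If PACE v kcal is not significant and the protocol advertises 0.80 power for any pair, the result is easily taken as evidence that the two labels work equally well.

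**Working it through.** **Inputs.** Alpha 0.05, power 0.80, an 8% difference, 18 trials per participant, and an SD of 300 kcal at each of two levels (section 7.9). Analysed sample 1,600, which is 400 per condition (section 7.9). Six pairwise contrasts per model: 3 + 2 + 1 (section 7.5). Half the sample in each education group (section 4.1), so 400/2 = 200 per arm within a stratum. Two-sided testing is assumed, since the plan does not state sidedness.

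**The plan's own figure.**
- SD of a participant's mean = sqrt(300² + 300²/18) = 308.2 kcal.
- SE of a difference between two arms = 308.2 × sqrt(2/400) = 21.8 kcal.
- Difference detectable with 0.80 power = (1.960 + 0.842) × 21.8 = 61.1 kcal.
- This equals 8% only if the control mean is 61.1/0.08 = 763 kcal.

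The plan gives no control mean. At assumed means of 500, 600, 700, 800 and 900 kcal, power for 8% would be 0.45, 0.60, 0.73, 0.84 and 0.91. The 0.80 can therefore be neither confirmed nor refuted. The 763 kcal is solved from the 0.80 and is not a check on it. The steps below take 0.80 at 8% as given.

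**Power at the levels used in section 7.5.** Power of 0.80 at two-sided 0.05 means that an 8% difference has an expected z of 1.960 + 0.842 = 2.802. A difference of r% has expected z = 2.802 × r/8, divided by sqrt(2) when the arms are halved. Power = Φ(expected z − critical value). The critical values are 1.960 at 0.05, 2.638 at 0.05/6 and 2.865 at 0.05/12.

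For a full 8% difference:
- 400 per arm, 0.05/6: Φ(2.802 − 2.638) = 0.56.
- 400 per arm, 0.05/12: Φ(2.802 − 2.865) = 0.47.
- 200 per arm, 0.05/12: Φ(1.981 − 2.865) = 0.19.

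Twelve is twice six, so the plan's example fits two stratified models, and the 200-per-arm line then applies.

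The smallest difference with 0.80 power is 8 × (2.638 + 0.842)/2.802 = 9.9% at 0.05/6 and 8 × (2.865 + 0.842)/2.802 = 10.6% at 0.05/12, with 400 per arm. Both exceed the cited 8.4% for kcal.

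**PACE v kcal, as a scenario.** If both cited reductions held on the same base, the gap would be 14.4 − 8.4 = 6.0 points. Expected z = 2.802 × 6/8 = 2.101. With 400 per arm:
- 0.05: Φ(2.101 − 1.960) = 0.56.
- 0.05/6: Φ(2.101 − 2.638) = 0.30.
- 0.05/12: Φ(2.101 − 2.865) = 0.22.

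If the 6.0 points are instead expressed relative to the kcal arm, they become 6.0/91.6 = 6.55%, and power is 0.63, 0.37 and 0.28 at the same three levels. A one-sided 0.05 test, with the stated 0.80 also read as one-sided, gives Φ((1.645 + 0.842) × 0.75 − 1.645) = 0.59 for 6.0 points. None reaches 0.80.

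Running the contrasts only after a labelling main effect adds a hurdle, so it cannot raise any of these figures.

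**The case against.** The sentence in section 7.9 states a detectable difference. With equal arms and one SD, every pair of groups has the same standard error, so an 8% difference is as detectable for kcal v PACE as for label v no label. At alpha 0.05 the sentence is valid on its own terms. That stands, and the words covering any of the four groups need not be removed.

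A reader might go further and infer that the plan's own figures put the PACE v kcal difference at 6.0%, so that the third hypothesis has 56% power. The documents do not support that. Section 7.9 never subtracts the two figures, and it sets the 14.4% aside. The two estimates come from separate meta-analyses of different kinds of eating occasion, and the comparator behind the 14.4% is not stated. The 6.0 points is a scenario and no more.

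A reader might also infer that using 8% for every label commits the plan to a zero difference between PACE and kcal. It does not: 8% is the size the study is meant to be able to detect, not a forecast that the labels act alike.

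It is also true that the corrected level is not a single number, that section 7.9 never says in terms that the third hypothesis is adequately powered, and that section 7.5 never says a null contrast will be read as equality. These points limit how strongly the criticism can be put. They do not answer the mismatch between 0.05 in section 7.9 and the divided level in section 7.5, which does not rest on the 6.0 points at all.

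**Conclusion.** The point holds as a mismatch between the stated power and the planned test. For a full 8% difference between two arms, the 0.80 falls to roughly 0.56 or 0.47 in the whole sample, depending on whether six or twelve comparisons are counted, and to 0.19 if the twelve are made within education strata. These figures rest on the stated 0.80 being right, on two-sided testing and on equal arms. For the within-stratum figure they also need the planned even split by education.

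For PACE v kcal there is the further gap that no cited effect supports a difference as large as 8 points. The conditional 6.0-point figures show the likely order of the problem, not the plan's expectation. Section 7.9 contains no calculation that is shown to be wrong. The power it reports is for a level that section 7.5 does not use for these contrasts, and the text should be changed to say so.

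**What to change.** - Section 7.9: keep the 8% sentence and say that it applies at an uncorrected alpha of 0.05. State the control mean used to turn 8% into kcal and whether the test is two-sided, so that the 0.80 can be checked.
- Section 7.9: add pairwise power for 8% at the levels used in section 7.5. On the present inputs this is about 0.56 at 0.05/6 and 0.47 at 0.05/12 with 400 per arm, and about 0.19 at 0.05/12 with 200 per arm.
- Section 7.9: add the PACE v kcal figures (6.0 points; about 0.56, 0.30 and 0.22 at 0.05, 0.05/6 and 0.05/12), labelled as a scenario that applies if both cited effects hold, not as the expected difference.
- Section 7.5: state that a non-significant PACE v kcal contrast will be reported with its confidence interval and not interpreted as equal effectiveness.

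These are wording changes with no extra participants and no change to the design. The cost is a less favourable stated power for the pairwise contrasts, including one primary hypothesis.

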9. APPENDIX A: FOOD STIMULI DESCRIPTION

FOOD	1 st picture 20 kcal	25 th picture 500 kcal	Last (50 th) picture 1000 kcal
Beef in black beans sauce with rice 130 kcal/100g	Beef 8.7 g Rice 6.7 g	Beef 217.6 g Rice 167 g	Beef 435.2 g Rice 334.0 g
Beef stew with dumplings 167 kcal/100g	Beef 8.07 g Dumplings 3.9 g	Beef 201.77 g Dumplings 97.6 g	Beef 403.53 g Dumplings 195.27 g
Chicken and bacon pasta 139 kcal/100g	14.4 g	359.7 g	719.4 g
Chicken, chips and beans 225 kcal/100g	Chicken 3.1 g Chips 4.2 g Beans 2.84 g	Chicken 80.5 g Chips 108.9 g Beans 74.05 g	Chicken 154.8 g Chips 209.5 g Beans 142.41 g
Chicken korma with rice 154 kcal/100g	Chicken 7.1 g Rice 5.9 g	Chicken 177.3 g Rice 147.4 g	Chicken 354.5 g Rice 294.8 g
Chicken salad 98.31 kcal/100g	Cucumber 7.3 g Salad 5.6 g Chicken 4.4 g Croutons 1.4 g Dressing 1.2 g Parmesan 0.5 g	Cucumber 182.3 g Salad 129.5 g Chicken 100.8 g Croutons 31.7 g Dressing 27.3 g Parmesan 10.8 g	Cucumber 364.5 g Salad 281.6 g Chicken 219 g Croutons 68.8 g Dressing 59.4 g Parmesan 23.5 g
Cous cous and salad 179.38 kcal/100g	Cous cous 10.2 g Salad 0.9 g	Cous cous 255.3 g Salad 23.4 g	Cous cous 510.6 g Salad 46.8 g
Fish, chips and peas 171.56 kcal/100g	Fish 3.25 g Chips 5.85 g Peas 2.54 g	Fish 81.44 g Chips 146.25 g Peas 63.74 g	Fish 162.88 g Chips 292.5 g Peas 127.50 g
Grilled white fish (41.24%) with tomato and bean salad 75.68 kcal/100g	Fish (cooked) 10.9 g Salad 15.5 g	Fish (cooked) 272.5 g Salad 388.1 g	Fish (cooked) 545 g Salad 776.3 g
Ham and mushroom carbonara 199 kcal/100g	10.1 g	251.3 g	502.5 g
Lasagne and peas (9.25%) 144.23 kcal/100g	Lasagne 11.9 g Peas 2.7 g	Lasagne 310.5 g Peas 70.73 g	Lasagne 597 g Peas 136 g
Macaroni cheese 183 kcal/100g	10.9 g	273.2g	546.4 g
Mushroom risotto 130 kcal/100g	15.4 g	384.6 g	769.29 g
Peperoni pizza 272 kcal/100g	7.35 g	183.82 g	367.64 g
Sausage (55.93%), mashed potatoes (33.55%) and peas (10.52%) 163.417 kcal/100g	Sausage 4.7 g Potatoes 9.7 g Peas 3.09 g	Sausage 122.2 g Potatoes 252.8 g Peas 80.44 g	Sausage 235 g Potatoes 486.2 g Peas 154.7 g
Spaghetti Bolognese 141 kcal/100g	14.1 g	354.61 g	709.2 g
Spinach & Ricotta tortellini with tomato sauce 316 kcal/100g	15.7 g (cooked)	393.4 g (cooked)	786.9 g (cooked)
Vegetable biryani 127 kcal/100g	15.7 g	393.7 g	787.4 g

10.

